**Mean change in severity of moderate to severe HF from baseline over time:**

This will be calculated as the difference in the severity of HF at various weeks, respectively, from the baseline value of the severity of moderate to severe HF.

#### **9.4.2.2 Primary analysis of the primary efficacy endpoints**

The primary estimand to be applied to primary efficacy endpoint is described in [Table 3-2](#).

The primary endpoint will be analyzed using a mixed model with repeated measures (MMRM) model on the change from baseline scores at various weeks including Week1, Week 4, Week 8 and Week 12. Baseline, treatment and Week will be included as covariates in the model. The interaction terms baseline\*Week and treatment\*Week will also be included. The primary endpoint is the treatment difference between the elinzanetant and placebo at Week 12. More details on model diagnostics, alternative modeling approaches, main and

sensitivity analysis, and details of the missing data handling/imputation will be given in the SAP.

#### **9.4.3 Secondary Endpoints**

The secondary efficacy endpoints in this study are:

- Mean change in PROMIS SD SF 8b total score from baseline over time
- Mean change in MENQOL total score from baseline over time

The calculation of the scores for PROMIS SD SF 8b, and for the MENQOL total score will be done according to the respective questionnaire guidelines. Details will be provided in the SAP.

The change from baseline for the secondary endpoints will be analyzed descriptively by treatment group using the number of non-missing observations, arithmetic mean and standard deviation, median, minimum and maximum using the FAS. In addition to the change from baseline over time, the values at various weeks will also be summarized accordingly.

#### **9.4.4 Exploratory / Other Endpoints**

The analysis of the exploratory / other safety and efficacy endpoints will be described in the SAP. Additional exploratory endpoints may be specified in the SAP.

#### **9.4.5 Other Safety Analysis**

All safety analyses will be descriptive and will be performed on the SAF. Safety data will be summarized descriptively for each treatment group.

All AEs will be coded using the latest version prior to data base lock of the Medical Dictionary for Regulatory Activities (MedDRA).

The percentage change from baseline in BMD in lumbar spine (total), total hip and femoral neck will be analyzed descriptively over time by treatment group in participants, who have BMD data available.

Further details on safety analyses will be described in the SAP.

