**Table 3-1: Objectives and endpoints**

Objectives	Endpoints
Primary	
Primary endpoint Mean change in frequency of moderate to severe HF from baseline to Week 12 (assessed by HFDD)
 
Exploratory endpoints
 
 
Mean change in frequency of moderate to severe HF from baseline over time (assessed by HFDD)
 
Mean change in severity of moderate to severe HF from baseline over time (assessed by HFDD)
 

Secondary	
Secondary endpoints:
 
 
Mean change in PROMIS SD SF 8b total score from baseline over time
 
Mean change in MENQOL total score from baseline over time
 
 
Exploratory endpoints:
 
 
Mean change in MENQOL VMS subscore from baseline over time
 
Mean change in body weight from baseline over time
 
Mean change in body composition from baseline over time
 

 
To evaluate the efficacy of elinzanetant on: 
 
sleep quality
 
menopause related quality of life
 
weight and body composition
 
 in women being treated for relief of VMS associated with the menopause
 
	
Other endpoints:
 
 
Number of participants with non-benign endometrial biopsy results
 
Mean percentage change in BMD from baseline to Week 52
 
Number of participants with TEAEs
 
Number of participants with abnormal laboratory parameters
 
Mean change in Sleepiness Scale at Week 1, Week 4, Week 12, Week 24, Week 36, Week 50 compared to baseline.
 

Other pre-specified	
 
Systemic exposure of elinzanetant in plasma via sparse PK sampling
 
Various biomarkers (e.g., diagnostic, safety, pharmacodynamic, monitoring, or potentially predictive biomarkers)
 

The full list of exploratory endpoints will be presented in the SAP.

BMD = bone mineral density, HFDD = Hot Flash Daily Diary, HF = Hot flashes, MENQOL=Menopause Specific Quality of Life Scale, PK = Pharmacokinetics, PROMIS SD SF 8b=Patient-reported Outcomes Measurement Information System Sleep Disturbance Short Form 8b, TEAEs = Treatment emergent adverse events, VMS = Vasomotor symptoms

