## 4.2 Scientific Rationale for Study Design

A double-blind placebo-controlled design is considered necessary to differentiate drug effects from the natural course of disease, the effects of study participation, and background safety findings. Experience from multiple studies of women with postmenopausal VMS have shown that a placebo response of up to 60% can be expected (Newton et al. 2014). Therefore, comparison to placebo is relevant to describe the true treatment effect of elinzanetant.

Placebo is considered acceptable because post-menopausal VMS are uncomfortable and disruptive to affected individuals, but not life-threatening or life-limiting. The use of placebo is also considered adequate by both the US FDA and EU Committee for Medicinal Products for Human Use (CHMP) disease-specific guidelines (EMA 2005, FDA 2003).

The study includes multiple safety and efficacy endpoints in a population of patients with different degrees of moderate to severe VMS with the intention of reflecting the future patient population. These assess relevant aspects for the treatment of women with VMS and safety topics that were identified based on the mode of action of elinzanetant as well as available pre-clinical and clinical data.

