Treatment decisions are made based on local DEXA assessment at the discretion of the investigator. Central DEXA assessment results will not be provided to the study sites.

All DEXA scans acquired for the study will be analyzed by an imaging technician at the central imaging laboratory. Central analysis of the DEXA scans will reduce the variability of the results. The DEXA analysis will provide BMD values, T-scores and Z-scores for each of the anatomic areas (lumbar spine, total hip and femoral neck) for all study DEXA visits. The BMD results from all DEXA visits will be used to calculate the % change in BMD over time for each participant. The expected bone loss for untreated post-menopausal women is presumably 1-2% per year ([Finkelstein et al. 2008](#)). Further details of the central DEXA review and analysis are described in the corresponding DEXA image review charter.

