## 5. Statistical Analyses

### 5.1 General Considerations

All variables collected in the study will be summarized using descriptive statistical methods. Continuous variables will be summarized using at least the following descriptive statistics: number of non-missing observations, arithmetic mean and standard deviation (SD), median, minimum and maximum. The geometric mean and geometric SD will be provided instead of the arithmetic mean and SD for variables where lognormal distributions are assumed. Categorical data will be summarized using frequency tables. Where appropriate, the data will also be presented by visit or week, including the analysis of the changes from baseline.

For the main analysis the type I error rate will be controlled at 2.5 % one-sided. Where appropriate two-sided 95 % confidence intervals (CIs) will be provided.

The statistical evaluation will be performed by using the software SAS (release 9.4 or higher; SAS Institute Inc., Cary, NC, USA).

Variables recorded in the electronic case report form (eCRF) and relevant derived variables will be shown in subject data listings, whereby only randomized participants will be included. Data from screening failures will only be shown in the 'Screening failure' listing.

Number of decimal places for summary statistics are shown in [Table 5–1](#). Derived variables would have maximum 1 decimal place and that value is considered as original data.

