#### **5.6.3.8 Bone mineral density**

Bone mineral density (BMD) will be analyzed using BMD Analysis Set (BAS). List of HRT and other drugs affecting bone density will be given in the Section [6.8](#).

Summary statistics for the percentage change from baseline in BMD of lumbar spine, total hip and femoral neck (using the central reading results) will be provided by treatment group and visit.

The time course by visit and by treatment group will be shown using line plots depicting the mean  $\pm$  95% plot for the percentage change from baseline in BMD of lumbar spine, total hip and femoral neck.

Percentage change in BMD of lumbar spine, total hip and femoral neck from baseline with frequencies and percentages for the following categories:  $<-6\%$ ,  $\geq-6\% - <-3\%$ ,  $\geq-3\% - <-1.5\%$ ,  $\geq-1.5\% - \leq0\%$ ,  $>0\% - \leq1.5\%$ ,  $>1.5\% - \leq3\%$ ,  $>3\% - \leq6\%$  and  $>6\%$  will also be summarized by treatment group and visit.

The Z-score and the T-score and the respective change from baseline in Z-score and T-score by BMD location will be summarized by treatment group for each visit using descriptive statistics.

Z-score and T-score with frequencies and percentages for the following categories:  $\leq -2$  -  $\leq -1.5$  ,  $> -1.5$  -  $\leq -1$  ,  $> -1$  -  $\leq 0$  ,  $> 0$  -  $\leq 1$  ,  $> 1$  -  $\leq 1.5$  ,  $> 1.5$  -  $\leq 2$  and  $> 2$  will also be summarized by treatment group and visit.

Participants that had at least one DEXA scan with either BMD loss  $> 6\%$  from baseline to Week 24/Week 52 for any location or Z-score  $\leq -2$  SD for any location will be listed.

If the baseline scan at Screening Visit 2 is missing or not evaluable based on the evaluation from the imaging central laboratory, the participant is requested to have a repeat scan. If it's not possible to have this repeat scan performed before the start of treatment, this repeat scan is allowed to be performed shortly after the start of the treatment (within maximum of 15 days). Considering the BMD will not change quickly, this can be accepted from a medical point of view. If a BMD value performed after the treatment start date has been flagged as baseline, it will be analyzed as baseline.

Both scheduled and unscheduled measurements can be used in the analysis. The following time windows apply, when re-mapping measurements to the visits:

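### The Week 52 bone mineral density endpoint is summarized arm by arm, with no elinzanetant-placebo difference or confidence interval, so the excess bone loss the trial can rule out is never stated.

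*Protocol*

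**What the plan says.** Protocol Table 3-1 lists "Mean percentage change in BMD from baseline to Week 52" among the other endpoints under the safety objective. Protocol 9.4.5 sets the general rule, "All safety analyses will be descriptive and will be performed on the SAF", and says that the percentage change at lumbar spine, total hip and femoral neck "will be analyzed descriptively over time by treatment group in participants, who have BMD data available".

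SAP 5.6.3.8 fills this in on the BMD Analysis Set:

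- "Summary statistics for the percentage change from baseline in BMD of lumbar spine, total hip and femoral neck", by treatment group and visit.
- A figure: "The time course by visit and by treatment group will be shown using line plots depicting the mean" with 95% bars. The text reads as mean ± 95% without the word CI; I take it as a 95% confidence interval, as in the SAP's other line plots.
- Eight categories of percentage change, and summaries and categories of Z-score and T-score.
- A listing of women with a loss above 6% or a Z-score of -2 or below.
- Scatter plots against baseline variables and boxplots by race.

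No elinzanetant-placebo difference, interval for a difference, model or margin is specified for BMD. SAP 1.1 and 5.3 specify a treatment difference for the primary endpoint only. The general sentence in SAP 5.1, "Where appropriate two-sided 95 % confidence intervals (CIs) will be provided", does not commit to one for BMD.

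Two other statements bear on this. Protocol 8.2.8: "The expected bone loss for untreated post-menopausal women is presumably 1-2% per year". Protocol 4.2 says the placebo design is needed to "differentiate drug effects from the natural course of disease, the effects of study participation, and background safety findings".

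**The concern.** By the protocol's own expectation, women on placebo lose bone during the year. A mean loss on elinzanetant is therefore not a signal in itself, and a mean loss on placebo is not reassurance. The quantity that answers the safety question is the difference between the arms, and Protocol 4.2 gives that kind of separation as the reason for having placebo. The plan collects the data for it, with central reading, phantom checks and one densitometer per woman, but does not specify the estimate.

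Without it, the report contains two by-arm means with separate bars. Comparing separate 95% bars by eye is a stricter criterion than an interval for the difference: with equal arms, bars that just touch correspond to a two-sided p of about 0.006. More important for safety, nothing in the planned output states how large an excess loss remains compatible with the data.

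**Working it through.** **What the plan gives.** There is no sample size, SD, power or precision for BMD. Table 9-1 concerns hot flash frequency only; its powers of 77.1%, 98.2% and >99.9% reproduce with the exact noncentral t (N = 270 per arm, SD 4.29, one-sided 0.025). The one-year figure in Protocol 9.2 also reproduces: 300 × 0.70 = 210.

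**Inputs**

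- 300 randomized per arm (Protocol 9.2).
- BMD in at least 50% of participants (Protocol 8.2.8): about 150 per arm.
- 30% one-year drop-out (Protocol 9.2). It is stated for the elinzanetant arm; I assume the same on placebo.
- Hence 150 × 0.70 = 105 per arm at Week 52, before the SAP's exclusions for bone-active drugs.
- SD of percentage change: not in the documents. Assumed 3 points, range 2-4.

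**Formulas**

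- By-arm half-bar: h = t(0.975; n-1) × SD/√n. Two equal bars overlap when the observed difference is below 2h.
- Half-width of the 95% CI for the difference: w = t(0.975; 2n-2) × SD × √(2/n).

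**At n = 105, SD 3:** h = 1.983 × 3/√105 = 0.58, so the bars overlap below 1.16. w = 1.971 × 3 × √(2/105) = 0.82. With 1.96 in place of t, these are 1.15 and 0.81.

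| SD (assumed) | Bars overlap below, n=105 | Difference CI half-width, n=105 | Bars overlap below, n=150 | Difference CI half-width, n=150 |
|---|---|---|---|---|
| 2 | 0.77 | 0.54 | 0.65 | 0.45 |
| 3 | 1.16 | 0.82 | 0.97 | 0.68 |
| 4 | 1.55 | 1.09 | 1.29 | 0.91 |

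The n = 150 columns show no drop-out at all, as an upper bound if exactly half are scanned.

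**Chance that the bars overlap, n = 105.** The observed difference is treated as normal with standard error SD × √(2/n).

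| True excess loss | SD 2 | SD 3 | SD 4 |
|---|---|---|---|
| 1 point | 21% | 65% | 84% |
| 1.5 points | 0.4% | 21% | 54% |
| 2 points | 0% | 2% | 21% |

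At SD 3 and a true excess loss of 1 point, the difference CI excludes zero in about 67% of trials, while the bars separate in only about 35%. In about 32% the bars overlap although the difference CI excludes zero.

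**Turning points, n = 105.** Setting 2h equal to the observed difference, a 1-point difference shows overlapping bars once the SD exceeds about 2.6, and a 2-point difference once it exceeds about 5.2. Setting w equal to 1 point, the difference CI also includes zero for an observed 1-point difference once the SD exceeds about 3.7.

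**Touching bars:** z = 2 × 1.96/√2 = 2.77, two-sided p = 0.0056.

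**The case against.** The strongest reply is that this is a consistent, pre-specified choice. Protocol 9.1 makes every endpoint but the primary descriptive, Protocol 9.4.5 does so for all safety analyses, and even the secondary efficacy endpoints have no contrast. That stands as a description of the plan. It does not rule out an estimate with an interval: no hypothesis is tested and no alpha is spent. BMD also has a particular claim to one, because the protocol itself predicts background loss.

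A reader might infer that the plan hides a drug effect as large as a year of natural loss. The documents do not support that. The stated loss is 1-2%. Over the assumed SD range of 2-4, an observed 2-point difference always separates the bars, and masking of 1 point depends on an SD the documents do not give. The by-arm n, mean and SD also let anyone compute an unadjusted difference and its interval. They do not yield a baseline-adjusted one.

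A reader might also infer that overlap will decide the bone safety conclusion, or that the plan leans toward finding no signal. Neither document sets an overlap rule or any other BMD decision rule, and the table specifications are in a separate document. The category tables, Z- and T-score tables and listing are real safeguards, but for distributions and individual women; none gives the mean excess loss.

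Two technical points stand. The BMD Analysis Set depends on available scans and on not using bone-active drugs after randomization, and is analysed by intervention received, so a contrast on it is not a clean randomized comparison. The figure of 105 is soft: 50% is a minimum target, while drug exclusions and the limit of 60 days after last dose for mapping scans reduce it.

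**Conclusion.** The point holds as a gap in the summary of a named safety endpoint. The plan describes each arm and leaves out the between-arm estimate that separates a drug effect from expected loss. The primary analysis is unaffected.

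Its size is moderate and conditional. With about 105 women per arm and an SD of 3 points, the difference would be known to about ±0.8 points, whereas by-arm bars overlap up to about 1.16. An excess loss near 1%, the lower end of the protocol's range, could be missed by eye; 2% usually would not be (2% chance of overlap at SD 3, 21% at SD 4). This rests on an assumed SD, on 50% scanned and on equal drop-out. Above an SD of about 3.7, sample size rather than presentation limits what an observed 1-point difference can show. The interval is still useful there, because it says openly that such a loss is not excluded.

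**What to change.** Add to SAP 5.6.3.8, for lumbar spine, total hip and femoral neck at Weeks 24 and 52, the elinzanetant-placebo difference in mean percentage BMD change with a two-sided 95% CI. Adjust for baseline BMD and region, by ANCOVA at each visit or one two-visit repeated-measures model per site. Densitometer make is optional: the outcome is within-woman change, with the same instrument intended for all her scans. State that this is estimation without a test, so the descriptive status and the no-multiplicity statement stay as they are. Label it as a contrast on the BMD Analysis Set, which is selected after randomization and analysed by intervention received.

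The cost is a paragraph of SAP text, one more table and a simple model per site, on data already collected. The intervals may be wide, and the label must make clear that this is not a clean randomized comparison.

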#### **9.4.6 Other Analysis**

Exploratory subgroup analyses using descriptive statistics will be provided for the primary and secondary endpoints by region. Further subgroup analyses including additional subgroups (e.g. by BMI) may be specified in the SAP.

### **9.5 Interim Analysis**

No interim analysis is planned for this study. Blinded data may be used for evaluation of psychometric and other measurement properties of PRO instruments.

## 10. Supporting Documentation and Operational Considerations

### 10.1 Appendix 1: Regulatory, Ethical, and Study Oversight Considerations

#### 10.1.1 Regulatory and Ethical Considerations

- This study will be conducted in accordance with the protocol and with the following:
  - Consensus ethical principles derived from international guidelines including the Declaration of Helsinki and Council for International Organizations of Medical Sciences (CIOMS) International Ethical Guidelines
  - Applicable ICH Good Clinical Practice (GCP) Guidelines
  - Applicable laws and regulations
- The protocol, protocol amendments, ICF, Investigator Brochure, and other relevant documents (e.g., advertisements) must be submitted to an IRB/IEC by the investigator and reviewed and approved by the IRB/IEC before the study is initiated.
- Any amendments to the protocol will require IRB/IEC approval before implementation of changes made to the study design, except for changes necessary to eliminate an immediate hazard to study participants. Any substantial modification of the protocol will be submitted to the competent authorities as substantial amendments for approval, in accordance with ICH Good Clinical Practice and national and international regulations.
- Protocols and any substantial amendments to the protocol will require health authority approval prior to initiation except for changes necessary to eliminate an immediate hazard to study participants.
- The investigator will be responsible for the following:
  - Providing written summaries of the status of the study to the IRB/IEC annually or more frequently in accordance with the requirements, policies, and procedures established by the IRB/IEC
  - Notifying the IRB/IEC of SAEs or other significant safety findings as required by IRB/IEC procedures
  - Providing oversight of the conduct of the study at the site and adherence to requirements of ICH guidelines, the IRB/IEC, and all other applicable local regulations

#### 10.1.2 Data Safety Monitoring Board

An independent data safety monitoring board (DSMB) will be established for the elinzanetant development program to perform ongoing safety surveillance. The DSMB will monitor the general safety of the ongoing Phase 3 trials and relevant additional data at an appropriate frequency as provided in the DSMB charter and make recommendations to the sponsor regarding steps to ensure the safety of the trial participants. Details will be described in the DSMB charter.

### 10.1.3 Liver Safety Monitoring Board

An independent liver safety monitoring board (LSMB) will be established for the elinzanetant development program to perform ongoing surveillance regarding hepatic safety. Independent hepatologists experienced in the assessment of drug induced liver injury (DILI) will conduct an independent review of available clinical data, i.e. blinded individual cases pertaining to elevated transaminases or other liver health markers on a regular basis. The LSMB will advise the DSMB and the sponsor whether the individual cases meet the criteria of a potential DILI, and whether any other actions are necessary to ensure participant safety. Details will be described in the LSMB charter. Case evaluations of the LSMB will be included in the ongoing safety surveillance of the DSMB (see Section 10.1.2).

### 10.1.4 Financial Disclosure

Investigators and sub-investigators will provide the sponsor with sufficient, accurate financial information as requested to allow the sponsor to submit complete and accurate financial certification or disclosure statements to the appropriate regulatory authorities. Investigators are responsible for providing information on financial interests during the course of the study and for 1 year after completion of the study.

### 10.1.5 Informed Consent Process

- The investigator or his/her representative will explain the nature of the study to the participants and answer all questions regarding the study.
- Participants must be informed that their participation is voluntary. Participants will be required to sign a statement of informed consent that meets the requirements of 21 CFR 50, local regulations, ICH guidelines, Health Insurance Portability and Accountability Act (HIPAA) requirements, where applicable, and the IRB/IEC or study center.
- The medical record must include a statement that written informed consent was obtained before the participant was enrolled in the study and the date the written consent was obtained. The authorized person obtaining the informed consent must also sign the ICF.
- Participants must be re-consented to the most current version of the ICF(s) during their participation in the study.
- A copy of the ICF(s) must be provided to the participants.

Participants who are rescreened are required to sign a new ICF.

